3.0 INVESTIGATIONAL PLAN

3.1 Study Design and Patient Follow-up

This is a prospective, non-randomized, multicenter, pivotal IDE study evaluating the Investigational Devices with the ST Monitoring Feature. The Analyze ST study is designed to demonstrate the safety and efficacy of the ST Monitoring Feature in the Investigational Devices. The sensitivity of the ST Monitoring Feature for detecting acute coronary syndrome events will be the primary efficacy endpoint. The primary safety endpoint will be assessed by reporting the percentage of patients who experience a false positive detection during the 12 months following a 3 month run-in period.

The goal of the 3 month run-in period is to:

1. Identify patients whose EGM rhythm or morphology is unsuitable for chronic ST monitoring
2. Provide data collection for review in order to adjust or optimize ST feature parameters

[figure not shown]
Data collection for the purposes of the FDA market approval application will be considered to be complete when the primary safety endpoint data are available and at least 41 clinical events have occurred. It is estimated that up to 5,228 patients at

Statistical Analysis Plan

approximately 200 centers will be enrolled in the study with a follow up of 12 months to meet the primary study endpoints.

A flow diagram of the study design is below.

Study Flow Diagram

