A comparison of baseline characteristics of the subjects with missing data and those without missing data will be done to determine if there is evidence that the data are not missing at random (it is not possible to determine that data are missing at random). If the missing at random assumption is clearly violated by these comparisons, it is usually possible to find a sub-group that are not missing at random who have to be imputed differently, such as assigning the worst score to patients in the sub-group. If this resolves the missing at random difficulty, the sub groups will be given special scores and the remaining patients will be imputed as described above.

This analysis will use the patients from the complete case analysis to perform a logistic regression and an imputation procedure to impute false positive status for patients who were non-evaluable in the complete-case analysis. The imputations are described as follows: A logistic regression will be performed using the complete case patients, with the dependent variable dichotomous

Statistical Analysis Plan

false positive status and the independent variables for ischemic Cardiomyopathy and each of the four categories of non-ischemic Cardiomyopathies (Dilated, Hypertrophic, Restrictive and ARVD), age, gender, QRS duration > 120ms and EF% at the time of enrollment. The estimates of the coefficients and standard errors of the logistic regression will be used as the parameters of a multivariate normal distribution that will define the population of the logistic regression model parameters. Up to ten random samples logistic model parameters will be selected. For each random set of parameters, the non-evaluable patients will have their false positive status imputed as having experienced a false positive if their predicted logistic model response is >0.5, and not having experienced a false positive event otherwise. These imputed datasets will be created using PROC MI in SAS V9.2 or greater. An analysis of the hypothesis will be carried out for each complete imputed dataset, and the results will be combined across datasets to obtain one overall conclusion using PROC MIANALYZE in SAS V9.2 or greater.

Additional Analysis

[figure not shown]

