An empirical analysis will be provided for the proportion of patients experiencing false positive events using the estimator described in the Primary Analysis section. The standard error of this empirical estimate will be calculated as the standard deviation of a bootstrap distribution. The bootstrap distribution will be constructed using 1,000 bootstrap resamples. Each bootstrap resample will be performed at the patient level, and each resample will have a total sample size equal to the total number of evaluable patients. A two-sided 95% bootstrap confidence interval will be provided.

Subgroup Analysis

The analysis of the primary safety endpoint will be performed on the following the subgroups of patients

- Coronary artery disease patients with cardiomyopathy
- Coronary artery disease patients without cardiomyopathy
- Patients with abnormal baseline ECGs, for each of six abnormal subgroup categories
- Patients with normal baseline ECGs
- Patients with arrhythmias
- Gender
- Patients alerted via Merlin.net and patients alerted via device Patient Notifier

Sample Size

optimize ST feature parameters. The analysis with a 3-month run-in period

[REDACTED]

[REDACTED]

[REDACTED]

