4.7 Additional Analyses

The following additional data will be collected during the study:

- Demographic variables include: gender, age, ethnicity, cardiomyopathy classification, complete cardiovascular history, arrhythmia history, primary ICD indication, and EF% at the time of enrollment and QRS duration at baseline
- ST Diagnostic Data to include: heart rate at onset of the Type I ST episode, maximum ST shift during the Type I ST episode, Type I ST episode duration, total number of Type I ST episodes detected
- All diagnostic procedures (tests and interventions) stratified by investigator's assessment of whether the procedure would have been performed in presence and absence of ST diagnostic data

Statistical Analysis Plan

- Positive Predictive Value (PPV) of the ST Monitoring Feature
- Negative Predictive Value (NPV) of the ST Monitoring Feature
- Response rates to Patient Notifier and Merlin.net Type I ST Episode detections
- Cardiac medications (including anti-anginal medications) during clinical events
- CPK Isoenzymes, MB fractions and Troponin values collected during clinical events
- Stress test and 12-lead ECG measurements collected during clinical events
- Proportion of patients who have the ST Monitoring Feature turned off at every study visit from the Programming Visit onwards
- Adverse events
- Clinical events
- Spontaneous arrhythmic episodes
- Hospitalizations
- Mortality/Death

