4.7.2 ST Diagnostic Data

ST diagnostic data will be collected and presented for all Type I ST episodes for all patients with the Fortify[®] ST (upgraded), Fortify Assura[®] ST and Ellipse[®] ST devices. Additionally, ST diagnostic data from all patients with the Fortify[®] ST prior to being upgraded will be collected and presented.

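### The only specified imputation model for the primary safety endpoint omits run-in Type I episodes, baseline ECG class and arrhythmia history, so it cannot adjust for drop-out related to them

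*Protocol*

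**What the plan says.** The primary analysis in 4.3.2 is complete-case. A patient lost before the 12-month visit without a false positive is omitted, and a patient who had one and then withdrew is kept. The test passes if the Wilson upper bound is below 15%.

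The Imputation Analysis in 4.3.2 then fills in the omitted patients. "A logistic regression will be performed using the complete case patients", with "independent variables for ischemic Cardiomyopathy and each of the four categories of non-ischemic Cardiomyopathies" and, completing the list, "Dilated, Hypertrophic, Restrictive and ARVD), age, gender, QRS duration > 120ms and EF% at the time of enrollment". Up to ten parameter sets are drawn. For each, a lost patient is "imputed as having experienced a false positive if their predicted logistic model response is >0.5, and not having experienced a false positive event otherwise".

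The same section also plans a comparison of baseline characteristics between patients with and without missing data. A sub-group judged not missing at random may be imputed differently, for example given the worst outcome. No variables, threshold or sub-group are named.

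Other sections show what is collected:
- Run-in (3.1): one aim is to "Provide data collection for review in order to adjust or optimize ST feature parameters".
- Type I episodes (4.7.2): "ST diagnostic data will be collected and presented for all Type I ST episodes for all patients".
- Baseline ECG (4.7.9): the CEC classes it as normal or abnormal, with six kinds of abnormality.
- Demographics (4.7): these include "arrhythmia history, primary ICD indication, and EF% at the time of enrollment and QRS duration at baseline".
- Subgroups for this endpoint (4.3.2): "Patients with abnormal baseline ECGs, for each of six abnormal subgroup categories", and patients with arrhythmias.

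**The concern.** An imputation model can correct selective loss only through variables that it contains. The listed model has nine terms. Four of them code non-ischemic cardiomyopathy, in a trial that requires documented coronary disease. None records whether the device had already logged Type I episodes in that patient, which is the variable closest in kind to the outcome. ECG class and arrhythmia are left out although the plan treats both as worth a subgroup analysis of this endpoint. If patients with run-in episodes leave more often and have more false positives later, the model gives those leavers the risk of patients who merely share their age, sex, QRS group, EF and cardiomyopathy type. The analysis would then not test the complete-case answer against that kind of loss.

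**Working it through.** **No plan figure to reproduce.** The safety sample-size text is redacted, and the readable text gives no expected false positive percentage and no loss rate. The enrolment of 5,228 is driven by the efficacy endpoint, and this point does not depend on it.

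**From the documents:** 15% limit, one-sided 2.5%, the covariate list, the complete-case rule and the 0.5 cut.

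**Assumed:** 5,000 patients; true 12-month rate 15.0%; 15% with a run-in Type I episode; loss 20% with an episode and 5% without; risk ratio RR of 2, 3 or 4.

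**Step 1, risk by group.** Without an episode q = 0.15/(0.85 + 0.15 RR); with an episode RR × q.

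**Step 2, everyone who leaves does so at the start.** Evaluable share = 0.15 × 0.80 + 0.85 × 0.95 = 0.9275. For RR 3:
- Observed false positives: 0.12 × 0.3462 + 0.8075 × 0.1154 = 0.1347 of all patients.
- Complete case: 0.1347/0.9275 = 14.52%.
- Draws without the run-in term: leavers get the average risk, so 0.1347 + 0.0725 × 0.1452 = 14.52%, the complete-case answer again.
- Draws with the term: 0.1347 + 0.03 × 0.3462 + 0.0425 × 0.1154 = 15.0%.
- Plan's cut: no leaver exceeds 0.5, so 13.47%.

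| RR | Risk with / without episode | Complete case, and draws without term | Draws with term | 0.5 cut, with or without a yes/no term |
|---|---|---|---|---|
| 2 | 26.1% / 13.0% | 14.73% | 15.0% | 13.66% |
| 3 | 34.6% / 11.5% | 14.52% | 15.0% | 13.47% |
| 4 | 41.4% / 10.3% | 14.36% | 15.0% | 13.32% |

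Simulation with ten imputations by draw (separate runs of 600, 1,500 and 2,000 trials per setting) wrongly met the 15% goal in about 7-9%, 16-18% and 23-26% of trials without the term, and in about 3% with it. With RR 1, adding the term made no material difference.

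**Step 3, leaving spread over the year at constant hazard.** Let λ = −ln(1 − risk) and μ = −ln(1 − loss). Observed false positives are λ/(λ+μ) × (1 − e^−(λ+μ)) and completers are e^−(λ+μ). For RR 3, summed over both groups, the complete-case rate is 0.1426/(0.1426 + 0.7928) = 15.24%. For RR 2, 3 and 4 it is 15.35%, 15.24% and 15.16%, all **above** 15.0%, because leavers who had a false positive are kept. A complete-case fit with the run-in term and draws then gives 15.6-15.7%, also too high. A model by month with the term and draws gives 15.0-15.1%.

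**Step 4, what the term does under the plan's own cut.**
- With only the listed covariates and assumed modest effects (4,500 patients), the highest predicted probability averaged 0.31-0.34. Nobody is imputed as a false positive.
- With a yes/no run-in term, the fitted risk in patients with an episode is 26%, 35% or 41% (early leaving), or 28%, 37% or 44% (spread leaving). None passes 0.5.
- In a wider grid of 18 assumed scenarios, a yes/no term changed nothing in 12. In the other 6, where risk with an episode was 60%, the result ended 0.04 to 3.7 points above the truth.
- A run-in count, with its distribution also assumed, moved the early-leaving result from 13.3-13.7% to 13.8-14.2%, against a truth of about 15.0%.
- A monthly model with the cut imputes no one. Even a 41.4% annual risk is 1 − 0.5862^(1/12), about 4% a month.

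**The case against.** A reader might infer stronger claims, which the documents do not support.

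- **That the plan has no other missing-data provision.** It has the baseline comparison with a worst-outcome option, and ECG class or arrhythmia history could enter there. It is unspecified and gives no route for adding a variable to the model, so it softens the point but does not remove it.
- **That the missing covariates are what disables the imputation.** Step 4 shows that the 0.5 cut does most of that. The covariates matter once status is drawn.
- **That the omission favours passing the 15% goal.** Step 3 shows the complete-case bias is downward with early leaving and upward with spread leaving.
- **That patients troubled by run-in alarms will leave.** Section 4.3.1 places Patient Notifier activation at the Baseline visit for Fortify Assura ST and Ellipse ST. Run-in episodes are therefore not shown to be alarms that patients noticed, and nothing links them to leaving.
- **That run-in episodes must predict later ones.** The run-in serves to find unsuitable patients and adjust settings, and for upgraded Fortify ST devices the record may predate the firmware change. Both may weaken the link.
- **That the error rates in Step 2 describe the trial's test.** They describe a supportive analysis done by draws, which the plan does not use.

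It is also fair that QRS above 120 ms partly covers one ECG category, and that gender and cardiomyopathy are themselves subgroup factors. Rhythm, ST-T changes, PVCs and voltage remain unrepresented.

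**Conclusion.** The point holds in a limited form. The covariate list omits three plausible predictors. ECG class and arrhythmia history are plainly collected. Availability of run-in Type I episodes follows from the purpose of the run-in in 3.1 and from 4.3.3, which restricts its count to events after Baseline. If these variables predict both leaving and later false positives, the specified imputation cannot correct for it. Under the assumed early-leaving pattern, the shortfall in an imputation by draws is 0.3 to 0.6 points at a true rate of 15.0%. With spread leaving the complete-case error is 0.2 to 0.35 points the other way. All loss rates, risk ratios and timings are assumptions. Adding the covariates alone, with the cut retained, would bring little change or an overshoot. What is at stake is the value of the supportive analysis as a check on the primary result, not the primary test itself.

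**What to change.** In 4.3.2, Imputation Analysis:

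1. Add the run-in Type I episode count, baseline ECG class and arrhythmia history to the model. State how the run-in record is defined for upgraded Fortify ST devices.
2. Replace the 0.5 cut by a random draw from each patient's predicted probability.
3. Use a model that respects time at risk, for example by month, imputing leavers only for months not observed. Do this only together with item 2.

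Merging the four non-ischemic cardiomyopathy terms and using QRS duration as a continuous value are optional.

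The cost is SAP wording and light programming, with no extra patients or visits. The supportive estimate may become less favourable. The primary complete-case test stays as it is.

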4.3.2 Primary Safety Endpoint

The ST Monitoring Feature will be evaluated by the percentage of patients with false positive events. The percentage of patients with false positive events is calculated as the number of patients who experience false positives divided by the number of evaluable patients. A False Positive occurs when a clinical event does not occur within 72 hours following a Type I ST episode.

The hypothesis is formally expressed as follows:

H_0 : Percent of patients experiencing a false positive event in 12 months $\geq 15\%$

H_a : Percent of patients experiencing a false positive event in 12 months $< 15\%$

The desired outcome is to reject the null hypothesis at the 2.5% significance level. The null hypothesis will be rejected at the 2.5% significance level if the

Statistical Analysis Plan

upper bound of the 95% confidence interval for the percent of patients experiencing false positive events is less than 15%. The upper confidence bound will be calculated using the Wilson score interval method.

Patient Group

All enrolled patients who have a successful implant or system revision, complete the baseline follow up visit and have the ST Monitoring Feature and Patient Notifier turned ON will be included in the evaluation of this study endpoint. Data collection towards the study endpoint will begin after the Baseline visit.

Further, the analysis population for the primary safety endpoint will be those subjects with the Fortify[®] ST (upgraded), Fortify Assura[®] ST and Ellipse[®] ST. Data from subjects with a Fortify[®] ST device prior to being upgraded will not be included in this analysis.

Analysis

Primary Analysis

The primary analysis will be a complete case analysis where patients who are lost to follow-up before completing their 12 month visit without experiencing a false positive event will be considered non-evaluable and omitted from the analysis of the endpoint. Patients experiencing a false positive event and withdrawing before the 12 month visit will be included in the analysis. The proportion of patients experiencing false positives will be estimated by the number of patients experiencing a false positive event divided by the number of evaluable patients.

Imputation Analysis

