4.5 Overall sample size and data cut-off

[figure not shown]
The total number of patients required for enrollment in order to satisfy the primary endpoints and the secondary endpoint is driven by the sample size requirement to satisfy the primary efficacy endpoint. Thus the total sample size required for this study is 5,228.

Data collection for the purposes of the FDA market approval application will be considered to be complete when the primary safety endpoint data are available and at least 41 clinical events have occurred.

Following submission of the clinical data, patients will continue to be followed until closure of the study for providing long-term follow up on the Investigational Devices.

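### The supportive imputation of the primary safety endpoint classifies missing patients at a predicted probability of 0.5 instead of drawing their outcome, so the missing-data check is biased low or unstable

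*Protocol*

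**What the plan says.** Section 4.3.2 tests whether the share of patients with a false positive in 12 months is below 15%, using the upper limit of a 95% Wilson interval (2.5% level). The deciding analysis is stated as "The primary analysis will be a complete case analysis where patients who are lost to follow-up before completing their 12 month visit" without a false positive are left out. By contrast, "Patients experiencing a false positive event and withdrawing before the 12 month visit will be included in the analysis".

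The Imputation Analysis then fits a logistic model to the complete cases, with cardiomyopathy type, age, gender, QRS duration above 120 ms and EF as predictors. "The estimates of the coefficients and standard errors of the logistic regression will be used as the parameters of a multivariate normal distribution", from which up to ten parameter sets are sampled. For each set a non-evaluable patient is "imputed as having experienced a false positive if their predicted logistic model response is >0.5, and not having experienced a false positive event otherwise". The datasets are analysed and combined into one conclusion. A sub-group judged not missing at random may be handled differently, "such as assigning the worst score to patients in the sub-group".

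The Additional Analysis in the same section is a patient-level bootstrap in which "each resample will have a total sample size equal to the total number of evaluable patients". It therefore does not address missing data. A figure is not shown there, so other checks cannot be excluded.

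**The concern.** An imputation should reproduce the spread of outcomes that the model predicts. A patient with a predicted risk of 10%, 20% or 40% should be positive in about that share of imputed datasets. Under the 0.5 cut such a patient is a certain non-event in every dataset. Sampling the coefficients varies the model but does not restore the missing outcome variation.

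Two things follow when the overall rate is near 15%. The imputed rate is pulled down, and the between-imputation variance is close to zero, so the standard error is too small. Both move the upper limit towards passing. The text also names coefficients and standard errors as the parameters of the multivariate normal and does not mention covariances, so two programmers could implement different procedures. At stake is the only missing-data analysis visible for a primary endpoint of a pivotal study.

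**Working it through.** **Inputs.** From the documents: goal 15%, 2.5% level, Wilson limit, the 0.5 cut, up to ten draws, the listed covariates (all section 4.3.2). N is bounded only from above: "Thus the total sample size required for this study is 5,228" (Protocol 4.5), and the safety group is "All enrolled patients who have a successful implant or system revision, complete the baseline follow up visit" with the ST Monitoring Feature and Patient Notifier on. Assumed, because the safety sample-size text is redacted: N of 1,000, 3,000 or 5,228; dropout of 5%, 10% or 20%; timing of loss; covariate distributions and effects.

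**The plan's own figure.** The level is (1 − 0.95)/2 = 2.5%. The Wilson upper limit is below 15% for at most 127/1,000, 411/3,000 or 733/5,228. At a true 15% with no missing data, the exact chance of passing is 2.1%, 2.3% and 2.4%. The stated level reproduces.

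**Limiting case by hand: every missing patient scored 0.** Take a constant false-positive hazard λ = −ln(0.85) = 0.1625 and a constant dropout hazard μ = −ln(1 − d). With E = 1 − exp(−(λ+μ)):

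- positive before loss: q = λ/(λ+μ) × E
- non-evaluable: m = μ/(λ+μ) × E
- complete-case rate: q/(1 − m)

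At d = 20%, μ = 0.2231 and E = 0.320, so q = 0.1348, m = 0.1852 and the complete-case rate is 0.1348/0.8148 = 16.5%. The true remaining risk of a non-evaluable patient is (0.15 − 0.1348)/0.1852 = 8.2%. Scoring 0 is therefore too low even after crediting the follow-up observed.

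| Dropout | All missing scored 0 | Complete case | Chance of passing, N = 1,000 / 3,000 / 5,228 |
|---|---|---|---|
| 5% | 14.6% | 15.3% | 4% / 8% / 11% |
| 10% | 14.3% | 15.7% | 8.5% / 20% / 32% |
| 20% | 13.5% | 16.5% | 25% / 65% / 88% |

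**The rule itself, full covariance matrix.** This was simulated with 1,200 trials per setting, ten coefficient draws, Rubin's variance and a Wilson bound at the effective N. Assumed covariates: ischemic cardiomyopathy 70%, dilated 6%, hypertrophic 1.5%, restrictive 1%, ARVD 0.5%; age 65 (SD 10); EF 30 (SD 9); male 80%; wide QRS 35%; linear-predictor SD 0.7.

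- Imputed positive: 0.03% to 3.1% of missing patients across settings. A separate simulation with other covariate effects, and loss unrelated to outcome, gave 0.05% to 4.0%.
- Mean rate at N = 3,000: 14.7/14.3/13.6% at 5/10/20% dropout.
- Passing at a true 15% and 20% dropout: about 19% at N = 1,000, and 53% and 59% in two separate runs at N = 3,000. Varying the linear-predictor SD from 0.4 to 1.0 gives 12.8% to 22.3% and 35.0% to 63.6%.
- Standard error at N = 1,000 and 20% dropout: 0.0111, against 0.0120 for a proper draw.
- Hazard shape at N = 3,000 and 20% dropout: a falling hazard moves the pass rate to 26%, a rising one to 74%.

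**Standard errors only, no covariances.** With age and EF uncentred and N = 1,000, 7% to 11% of missing patients are imputed positive on average, but 38% to 49% in the most extreme of ten draws. At 20% dropout the pooled standard error is 0.0326, about 2.7 times that of a proper draw (0.0326/0.0120), and the check passes 1.5% of the time (1.7% in a second run). At N = 3,000 it passes 13.6% (11% in the second run). With age and EF centred, the figures are 10.3% and 44.8%, so the answer turns on a coding choice the plan does not state.

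**Candidate repairs, true 15%.** A Bernoulli draw from the baseline model alone gives 15.3/15.7/16.5%: it removes the 0.5 cut but keeps the complete-case upward bias. A draw that also uses the event-free follow-up, and a Kaplan-Meier 12-month estimate, both centre on 14.9% to 15.1%. Under constant hazards they pass 1.3% to 2.9% and 1.5% to 3.0% of the time.

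**The case against.** The strongest reply is that nothing is decided here. The complete-case analysis is primary, and no text lets the imputation result overturn or rescue it. That stands, and it limits the point. A reader might infer that the rule inflates the study's false-positive decision rate; the documents do not support that. Complete case itself errs upward, against passing, when dropout is unrelated to outcome.

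A reader might also take it as proof of the flaw that, with the full matrix, the check never contradicted a complete-case pass in simulation. It is not. Under the same dropout a correct Kaplan-Meier check contradicted none either, because a complete-case pass is already conservative. Nor is every conflicting pass an error: at a true 13%, N = 3,000 and 20% dropout, complete case passed 14% of trials and Kaplan-Meier 84%.

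The bias is also about the size of the primary analysis's own. At N = 3,000 the imputed rate is off by −0.3/−0.7/−1.4 points and complete case by +0.3/+0.7/+1.6. That is fair, but a check that errs by as much the other way does not tell the reader where the truth lies.

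A multivariate normal implies a covariance matrix, so the literal standard-error reading may be only loose wording. Probably so, but one phrase would settle it. The worst-score provision could offset the lean, but only if a sub-group is first judged not missing at random.

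**Conclusion.** The rule is wrong as written and should be fixed. With the full covariance matrix it biases the imputed rate and its standard error downwards. With standard errors taken literally it is erratic, with no lean towards passing at N = 1,000, so a lean in every case cannot be claimed. In neither case does agreement or disagreement with the complete-case result say much about robustness. The primary decision is unaffected.

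The direction under the full matrix is firm. The size is not: it rests on assumed N, dropout, covariate strength and hazard shape, and on loss unrelated to unseen false positives. At 5% dropout the bias is only about 0.3 points, and if most losses come close to month 12 it shrinks further.

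**What to change.** In section 4.3.2, Imputation Analysis, replace the sentence with the 0.5 cut by: *For each draw of the model coefficients from their full estimated covariance matrix, each non-evaluable patient's status will be a Bernoulli draw, with the probability of a first false positive by 12 months given the listed covariates and the false-positive-free follow-up already observed.* That probability can come from a time-to-first-false-positive model, for example piecewise exponential, fitted to the whole analysis population. Combine across datasets as planned.

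A simpler alternative, or an addition, is a Kaplan-Meier 12-month estimate of time to first false positive with its 95% confidence interval, which needs no hazard shape. Keep the worst-score option, because both repairs assume dropout is unrelated to unseen false positives.

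The cost is a few sentences in the SAP and no new data: the secondary safety endpoint (section 4.3.3) already needs false positive dates and follow-up time. The downsides are a less favourable imputed rate, a slightly wider interval than the full-matrix rule gives and, for the model-based draw, an assumption about the hazard over time.
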